Odontoid fractures are the most common spinal fracture in elderly patients. Type II fractures which involve the waist of the dens are the most common, but heal least reliably due the watershed vascularity of this area, as well as low intrinsic stability of common fracture patterns. Non-union after non-operative treatment is even more prevalent (up to 85%) in an elderly population. Odontoid non-union can be a source of neck pain and disability, and less commonly cervical spine instability or progressive myelopathy/neurologic decline. Operative treatment with C1-2 fusion restores spinal stability and leads to more reliable union rates (>90%); however, major

perioperative complications occur in ~40% of patients¹. Given the significant morbidity and mortality associated with both operative and non-operative modalities, treatment of type II odontoid fractures in the elderly remains controversial.

Recent data from the AO Spine North American Geriatric Odontoid fracture study has suggested a survival benefit, particularly for younger elderly patients, who undergo operative stabilization of their odontoid fracture². The reason for this isn't fully understood, but is presumed to derive from achievement of stable bony union and its positive effect on pain, function, and possibly neurologic protection. If this stable bony union were able to be achieved more reliably without the risks of surgery in such a fragile population, that would represent a major advancement in care.

Parathyroid hormone analogs (e.g. teriparatide or abaloparatide) have been shown in multiple animal fracture models to have an anabolic effect on bone healing, however existing clinical data to date has produced conflicting results³. Peichl, et al. (2011) showed faster radiographic union rates in pubic bone fractures treated with PTH (7.6 wks) vs. control (12.8 wks), and Aspenberg et al. (2010) showed faster radiographic healing of distal radius fractures compared to placebo with 20ug dosing but no effect with 40ug dosing^{4,5}. A further study looking at femoral neck fractures did not show similar treatment effects with PTH treatment⁶. There remains significant uncertainty about which fracture types may respond to treatment, as well as the dose-response relationship.

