Statistical Considerations: Delineate the precise outcomes to be measured and analyzed. Describe how these results will be measured and statistically analyzed. Delineate methods used to estimate the required number of subjects. Describe power calculations if the study involves comparisons. Perform this analysis on each of the primary and secondary objectives, if possible.

Primary outcome will be % bridging bone on CT scan at 12 weeks as described previously based on 1 mm sagittal and coronal cuts. The study radiologist evaluating the primary outcome will be blinded to patient group (treatment vs. historical control). Secondary outcomes will include VAS Neck and NDI scores, and motion on flexion/extension radiographs.

Assuming 60% nonunion rate in our historical control group and 20% in our study group, with alpha = 0.05 and 80% power, we would need to enroll 44 patients in a randomized trial (22 control, 22 study patients) to show a statistical difference. This study is intended as an initial pilot study to suggest efficacy, and further inform a future randomized controlled trial. We see 15-20 new type II dens fractures treated non-operatively per year in our fracture clinic, and estimate the initial pilot of 10 treatment patients + 12 control subjects can be completed within 2 years.

Data analysis will be based on multi-variate regression using ANOVA, with $p < 0.05$ recognized as a significant difference. Plan is for as treated analysis; if there are patients who receive only partial course of study drug for any reason, they will be evaluated descriptively as a separate group. Additionally, we will also compare our study group results to the union rates documented in the existing literature.

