	Monthly		Annually
	Quarterly		Other (e.g. by dosing level, no. of subjects enrolled):
	Bi-annually		

Will the sponsor be conducting data monitoring visits for this study?

Yes No NA

If yes, how often?

--

Adverse Event, Unanticipated Problem (UAP), Reportable New Information (RNI): Describe how events and UAPs will be evaluated and reported to the IRB. All protocols should specify that, in the absence of more stringent reporting requirements, the guidelines established in the “Adverse Event and Unanticipated Problems Reporting Policy” will be followed. The UVM/UVM Medical Center process for review of adverse events and UAPs to subjects or others should be included in the DSMP.

Regular monitoring for adverse events will be performed via weekly phone calls and monthly clinic visits (Table 1) throughout the 12-week study period.

The guidelines established in the UVM IRB’s “Adverse Event and Unanticipated Problems Reporting Policy” will be followed. Adverse events include any unfavorable medical occurrence/sign/symptom that a patient experiences while participating in the study, whether these events are considered related to the study medication or not. Pre-existing conditions that do not worsen during the study will not be considered adverse events.

All adverse events and serious adverse events will be classified as expected vs unexpected; and classified as probably related to the study medication or not.

The following will be classified as serious adverse events based on the PI’s judgement and following the UVM IRB’s guidelines: any untoward medical occurrence that results in death or is life-threatening, requires inpatient hospitalization or prolongation of existing hospitalization, leads to persistent or significant disability and/or incapacity, causes a congenital anomaly and/or birth defect, or requires medical intervention to prevent any of these outcomes.

Withdrawal Procedures: Define the precise criteria for withdrawing subjects from the study. Include a description of study requirements for when a subject withdraws him or herself from the study (if applicable).

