Under routine care, patients with dens fractures are monitored for any fracture displacement using x-rays or neurologic changes that require a change in treatment plan. Study participants will be monitored in the same way. For treatment subjects: if the fracture clinic physician [name] has any concerns for abnormal fracture displacement or new neurologic deficit, the PI (or another fellowship-trained orthopaedic or neurologic spine surgeon on the study team as delegated by the PI) will review all radiographic evidence of fracture displacement or neurologic deficit. Based on fracture displacement and neurologic changes, the patient may require a change in their treatment plan. Study patients are treated no differently from non-study patients in this regard. If there is a significant change in their treatment plan (e.g. surgery), these patients will be withdrawn from the study at the discretion of the PI.

All study participants may voluntarily withdraw themselves from the study at any time. If a participant decides to withdraw, the study will continue to use the information already collected for the study before withdrawal. This is noted in the informed consent forms for both control and treatment subjects.

If a patient were withdrawn from the study for any reason, the standard of care treatment for their fracture would resume.

Sources of Materials: Identify sources of research material obtained from individually identifiable human subjects in the form of specimens, records or data. Indicate whether the material or data will be obtained specifically for research purposes or whether use will be made of existing specimens, records or data.

Sources of research information will be provided in the electronic health records (including imaging) and study questionnaires. This information will be used for eligibility screening, safety monitoring, primary outcome (CT scans) and secondary outcome (radiographs, VAS and NDI) measures. Material will be derived from both existing sources in the electronic health record and research-driven procedures. Together these materials include:

For treatment subjects

- Lab results and office notes
- Office notes from clinical exams and consultations, including VAS Neck and NDI measures
- Radiographs and CT scans
- Drug diary

For historical comparison subjects (Control cohort A: active control participants)

- Lab results and office notes
- Study questionnaires (VAS Neck and NDI)
- Radiographs and CT scans

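### Investigator-initiated withdrawal from the study after a change in fracture treatment can end adverse-event capture and the week-12 CT without any withdrawal of consent

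*Combined protocol and SAP*

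**What the plan says.** Withdrawal Procedures describes two routes out of the study.

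- **Investigator-initiated.** Treated patients are watched for displacement and new deficit, and "Based on fracture displacement and neurologic changes, the patient may require a change in their treatment plan". If that change is significant (surgery is the one example), "these patients will be withdrawn from the study at the discretion of the PI". What they leave is the study, not only the drug.
- **Voluntary.** A separate paragraph covers participants who decide to leave. The first route therefore operates without withdrawal of consent.

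On what follows, the section says only: "If a patient were withdrawn from the study for any reason, the standard of care treatment for their fracture would resume". It mentions no further study contact, safety follow-up or outcome assessment.

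The section on adverse events and reportable information says: "Adverse events include any unfavorable medical occurrence/sign/symptom that a patient experiences while participating in the study". It adds: "Regular monitoring for adverse events will be performed via weekly phone calls and monthly clinic visits (Table 1) throughout the 12-week study period". It does not say whether that monitoring continues for a patient who has been withdrawn.

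Table 1 marks the week-12 cervical CT as research-driven, and the notes under the table say the same. Statistical Considerations makes percent bridging bone on that CT the primary outcome, in a pilot of 10 treated patients and 12 controls.

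**The concern.** The events that lead to investigator withdrawal, displacement and neurologic change, bear directly on whether the treatment has failed. A rule that can end participation at that point selects on outcome. The form asks for precise withdrawal criteria, and the answer is discretion with one example, exercised by an investigator who knows the patient is treated.

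Two kinds of information are at stake. The first is safety after the change of treatment: a later complication, neurologic decline or death would not meet a definition tied to participation, even soon after a dose. The drug is not approved for this intended action (Drug Information). Data Safety and Monitoring has no independent board, reviews annually, and would consider modification or termination on repeated severe events attributed to the drug. Events outside the definition may not reach that review. The second is the primary outcome: routine collar care does not include the week-12 CT, so a scan not done at week 12 cannot be recovered later. The pilot is meant to inform a randomised trial, and the treated failures are among the most useful things it can report.

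**Working it through.** **The plan's own figure.** Statistical Considerations gives 44 patients (22 per arm) for nonunion of 60% versus 20%, alpha 0.05 and 80% power. With a two-sided test, pooled variance and no continuity correction:

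n per arm = [1.960·√(2·0.4·0.6) + 0.842·√(0.6·0.4 + 0.2·0.8)]² / 0.4² = (1.358 + 0.532)² / 0.16 ≈ 22.3

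Rounded up this is 23 per arm, or 46 in total. At 22 per arm the power is 79.4%. The stated 44 is therefore reproduced to within 2 patients. The present point does not depend on it, and the fix does not change it. The plan states no allowance for dropout.

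**Reading the sections together.**

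1. Withdrawal Procedures: a significant treatment change can lead to removal from the study with consent intact.
2. Adverse-event section: an event counts if it occurs during participation. The displacement or deficit that starts the process occurs before withdrawal, so it counts. Events after withdrawal do not.
3. Table 1 and its notes: the week-12 CT is done only for research, so a patient receiving only standard care would not be expected to have it.
4. No section restores either item after step 1, and none says how a withdrawn patient without a CT enters the primary analysis.

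**Scale.** The documents give no rate of treatment change, so the number withdrawn is an assumption throughout.

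Each patient is 1/10 = 10% of the treated arm. If f of 10 treated patients truly fail to unite, and k of those are withdrawn before the CT, observed nonunion is (f − k)/(10 − k).

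| True failures | Withdrawn before CT | Observed nonunion |
|---|---|---|
| 2/10 (20%, the plan's assumed treated rate) | 1 | 1/9 = 11% |
| 2/10 (20%) | 2 | 0/8 = 0% |
| 4/10 (40%) | 1 | 3/9 = 33% |
| 4/10 (40%) | 2 | 2/8 = 25% |
| 4/10 (40%) | 3 | 1/7 = 14% |

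The primary outcome is continuous, so the same point can be put as a mean. If completers average m% bridging and the k withdrawn patients would have shown none (an extreme case), the mean over all treated patients is m·(10 − k)/10. For an assumed m of 60%, that is 54% with one withdrawn and 48% with two.

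**Time at risk.** If treatment changed about 4 weeks after injury, the 12 (+/-1)-week visit would be 11 − 4 = 7 to 13 − 4 = 9 weeks away.

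**The case against.** The strongest reply is that no sentence says capture or the CT stops. Monitoring is set for the whole 12-week period, withdrawal is discretionary, and Sources of Materials names the health record as a source for safety monitoring. The institutional reporting policy that the plan adopts is not among the documents and may require some later reporting. All of this is fair. It makes the loss possible rather than certain, and it means the policy could fill part of the safety gap. It does not supply the week-12 CT, and it leaves what is kept to case-by-case judgement.

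A second reply is that after surgery, bridging bone no longer measures drug plus collar. That stands in part, and is why the CT should be kept only where it is still informative. It does not apply to safety data, or to counting the conversion itself.

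Several stronger readings are tempting, but the documents do not support them:

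- **That chart outcomes go uncollected.** The record is a named source with no stated cut-off at investigator withdrawal. The sentence limiting use to data gathered before withdrawal follows the participant's own decision to leave and does not govern this route.
- **That Statistical Considerations is contradicted.** It says of patients with a partial drug course that "they will be evaluated descriptively as a separate group". That concerns drug exposure and does not promise each of them a CT. It also shows that the plan already contemplates stopping drug without leaving the study.
- **That the Purpose section's perioperative complication rate measures the events missed.** It is a rate for surgery, no conversion rate is given, and every complication would have to fall after withdrawal took effect.
- **That the comparison is biased in favour of the drug.** Historical controls must have completed 12 (+/-1) weeks of collar (Inclusion/Exclusion Criteria), so control patients who changed treatment early are also left out.

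**Conclusion.** The concern holds in a limited form. Read as written, the plan allows a consenting treated patient whose fracture treatment changes to be removed from the study, after which later adverse events fall outside the definition and the primary-outcome CT need not be done. The event that prompted the change is itself captured.

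The loss is 10% of the treated arm per patient. In the illustration, a true 20% nonunion would be seen as 11% or 0%. This rests on an assumed number withdrawn, on those patients being true failures, and on withdrawal before the CT. Within the treated arm it would make the results look better than they are. Against the controls, the net direction is uncertain. The conclusion that follow-up ends is an inference from the wording and from silence on follow-up. The plan should be corrected on this point, but the design does not fail because of it.

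**What to change.** Change data collection only; no patient's treatment is altered.

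- **Withdrawal Procedures.** Separate a change in fracture treatment or stopping study drug from withdrawal of consent. State that only withdrawal of consent ends data collection.
- **Adverse-event section.** Replace the participation wording with a window from first dose through the 12 (+/-1)-week visit, for every dosed patient who has not withdrawn consent.
- **Outcomes.** Record each conversion with its date and report it as an outcome among all treated patients. Take available week-12 films and VAS Neck and NDI scores from the chart. Obtain the planned week-12 CT where it is feasible and still informative.

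The cost is revised wording in two sections, with matching consent language if needed (the consent form is not among the documents), and a few extra chart reviews or calls. The CT is already planned for each treated patient. One practical limit remains: visits after surgery may not follow the collar-care schedule, so some week-12 films and questionnaires may be missing or off schedule.

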The study will be introduced to the patient by a PI-delegated provider from the study team either during hospitalization or at their first visit to the spine fracture clinic – typically within 2 weeks of injury. Informed consent for this study may thus be obtained at one of two locations: (1) A majority (~75%) of these patients are admitted to the hospital; these patients will be introduced to the study by a PI-delegated provider who is key personnel on the study team, and may be consented while in the hospital. (2) Other patients may be identified and recruited from our Orthopedic Spine Fracture clinic, which is the referral repository for all non-operatively managed spine fractures within our health system.

Patients with acute Anderson & D'Alonzo type II dens fractures, +/- C1 ring injury, identified on cervical CT scan, and recommended for non-operative treatment will be recruited for enrollment in the study (see Inclusion/Exclusion Criteria, below). Acuity of the fracture will be determined by radiographic appearance, pain, and mechanism. Type II fractures are defined as described by Grauer et.al as involving the area of the dens between the inferior aspect of the anterior C1 ring and not extending into the superior articular facets of C2.⁹

If a patient consents to participation in the study, baseline labs will be drawn (see Table 1). The study team's endocrinologist will review labs and confirm their eligibility for the study. Lab values obtained during the screening process (see Screening Procedures below) could exclude patients include an elevated PTH or hypercalcemia. Given the medical complexity, there will not be hard cutoff values for the labs (see Inclusion/Exclusion Criteria, below) – but rather eligibility to participate will be left to the clinical judgement of our endocrinology investigator ([name] or another fellowship-trained endocrinologist in her absence who is key personnel on the study).

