For historical comparison subjects, the questionnaires will be administered by designated study personnel in person at UVMMC. The questionnaires will be completed by the patient after written informed consent is obtained.

TYPES OF PROCEDURES (Please do not use the "other" option unless the procedure is not listed.)

Check all that apply.

	Survey (mail, telephone, in-person, on-line)		Blood drawing:	Vol. 	Over days, weeks? 	Blood will be drawn for eligibility screening, and HbA1c levels in treatment subjects only
	Medical exams/history				Type & Amt. 	See the tests listed for treatment subjects in Table 1, above.
	Deception *see below		Surgery			Collection of Urine and/or Feces
	Observation		Drug Administration			HIV Testing
	Photographs		Device Use			Ultrasound (e.g. echocardiogram)
	Audio Recording		Exercise			X Imaging (e.g. CT scan, DEXA, mammogram, PET scans, SPECT)
	Video Recording		Diet			Use of Radiation treatment
	Interviews in person or by phone		Pathology Specimens (retrospective)			Use of Radioactive substances (e.g. radiolabeled antibodies, drugs or contrasts)
	Focus Groups		Genetic Materials (DNA)*			MRI (for treatment studies)
	Review of prospective data		Questionnaires			MRI (not for treatment studies)
	Review of retrospective data		Diaries			Tissue (obtained for clinical purposes)
	Recording of Identifiable Data		Pregnancy Tests			Tissue (obtained solely for research)
	Electrocardiograms					
	Sensitive Data (criminal or sexual conduct, drug or alcohol conduct or use)			(specify): 		

*If genetic information is being collected, GINA language must be added to the consent form.

*Deception typically involves withholding information from the potential subject and would require an alteration to the consent process.

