For historical comparison subjects (Control cohort B: review-only control participants)

- Lab results and office notes (incl. eligibility criteria, demographic information, and dens fracture characteristics)
- Radiographs
- VAS Neck and NDI measures, if they were recorded at routine care visit in the past

DRUG INFORMATION

Investigators are encouraged to consult the UVM Medical Center Investigational Pharmacy Drug Service ([name]) prior to finalizing study drug/substance procedures.

Drug (s)

Not applicable

Drug name – generic followed by brand name and common abbreviations. Availability – Source and pharmacology; vial or product sizes and supplier. If a placebo will be used, identify its contents and source.

Abaloparatide (TYMLOS)

Preparation: Reconstitution instructions; preparation of a sterile product, compounded dosage form; mixing guidelines, including fluid and volume required. Identify who will prepare.

TYMLOS injection is supplied as a pre-assembled single-patient-use disposable pen (NDC70539-001-01) packaged in a cardboard carton (NDC 70539-001-02) with the Instructions for Use and Medication Guide. Each disposable pen embodies a glass cartridge that contains 3120 mcg of abaloparatide in 1.56 mL (2000 mcg/mL) of sterilized, clear, colorless fluid. Each pen provides a 30-day supply for once daily injection of 80 mcg abaloparatide in 40 mcL. Sterile needles will be provided by the study.

Storage and stability – for both intact and mixed products.

Before first use, store TYMLOS in a refrigerator between 2°C to 8°C (36°F to 46°F).

After first use, store for up to 30 days at 20°C to 25°C (68°F to 77°F).

Do not freeze or subject to heat.

The medication will be stored at UVMMC in a refrigerator between 2°C to 8°C (36°F to 46°F) prior to use. It will be dispensed by the pharmacy for all participants for whom eligibility confirmation and consent are obtained at the inpatient setting. For subjects who are not consented and/or for confirmed as eligible until they are treated in the outpatient setting, the study drug will be picked up by a member of the research team and transported to the outpatient clinic for the time of drug teaching.

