No. However, the proposal involves use as an experimental treatment of a fracture that is most common in elderly patients with osteoporosis, and the study drug is approved for the treatment of individuals with osteoporosis who are at high risk for these fractures.

SUBJECT CHARACTERISTICS, IDENTIFICATION AND RECRUITMENT

Subject Selection: Provide rationale for subject selection in terms of the scientific objectives and proposed study design.

The study population includes patients greater than or equal to the age of 50. This is the population that sustains dens fractures most frequently.

Vulnerable Populations: Explain the rationale for involvement of subjects (e.g., cognitively impaired, Non-English speaking, prisoners, students). Discuss what procedures or practices will be used in the protocol to minimize their susceptibility to undue influences and unnecessary risk (physical, psychological, etc.).

Not applicable

Inclusion/Exclusion Criteria: Eligibility and ineligibility criteria should be specific. Describe how eligibility will be determined and by whom. Changes to the eligibility criteria at a later phase of the research have the potential to invalidate the research.

Treatment Subjects

Inclusion Criteria (all must be yes)

1. Age 50 years or older at time of consent
2. Anderson and D'Alonzo type II dens fracture identified on cervical spine CT, with or without a C1 ring injury. Type II dens fractures are defined as involving the area of the dens between the inferior aspect of the anterior C1 ring and not extending into the superior articular facets of C2.
3. Fracture is deemed amenable to non-operative treatment by treating fellowship trained spine surgeon
4. Fracture occurred within the 3 weeks before consent
5. Report of ≥ 12 months of amenorrhea within the last year if the patient is female

Exclusion Criteria (all must be no)

6. Personal history of radiation therapy to the skeleton
7. Personal history of osteosarcoma
8. Personal history of Paget's disease
9. Personal history of bone metastases or skeletal malignancy
10. Hereditary disorders predisposing to osteosarcoma
11. Prior teriparatide or abaloperatide use
12. Use of denosumab within the past year
13. Psychological impairment that precludes following hard collar immobilization recommendations
14. Ineligible based on history of active or recurrent kidney stones, CMP, PTH, Phos results to be determined on a case-by-case basis by an endocrinologist on the study team

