Historical Comparison Subjects

Inclusion Criteria (all must be yes)

1. Age 50 years or older at time of fracture
2. Anderson and D'Alonzo type II dens fracture identified on cervical spine CT, with or without a C1 ring injury. Type II dens fractures are defined as involving the area of the dens between the inferior aspect of the anterior C1 ring and not extending into the superior articular facets of C2.
3. Fracture injury occurred within 10 years before consent
4. The patient completed 12 (+/- 1) weeks of hard collar immobilization

Exclusion Criteria (all must be no)

5. Any history of prior teriparatide or abaloperatide use
6. Use of denosumab in the past year

Inclusion of Minorities and Women: Describe efforts to include minorities and women. If either minorities or women are excluded, include a justification for the exclusion.

Women will be included in the study whenever the eligibility criteria are met. Every effort will be made to recruit minorities. Recruitment efforts will not differ by sex or by ethnicity.

Inclusion of Children: Describe efforts to include children. Inclusion is required unless a clear and compelling rationale shows that inclusion is inappropriate with respect to the health of the subjects or that inclusion is inappropriate for the purpose of the study. If children are included, the description of the plan should include a rationale for selecting or excluding a specific age range of children. When included, the plan must also describe the expertise of the investigative team in working with children, the appropriateness of the available facilities to accommodate children, and the inclusion of a sufficient number of children to contribute to a meaningful analysis relative to the purpose of the study. Provide target accrual for this population. Identify whether children are wards of the state. **If children are excluded** then provide appropriate justification.

The fracture of interest occurs very rarely in minor subjects, and the safety and effectiveness of the study drug has not been established in pediatric patients. Children will not be included in this study.

For protocols including the use of an investigational drug, indicate whether women of childbearing potential have been included and, if not, include appropriate justification.

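### Exclusions 6–10 and 14 apply to treated patients only, so treated patients and historical controls are selected by different rules, with a bias of unknown size and sign

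*Combined protocol and SAP*

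**What the plan says.** **Treated group.** In the Inclusion/Exclusion Criteria for Treatment Subjects, exclusions 6–10 remove patients with skeletal radiation, osteosarcoma, Paget's disease, bone metastases or skeletal malignancy, and hereditary disorders predisposing to osteosarcoma. Exclusion 14 reads "Ineligible based on history of active or recurrent kidney stones, CMP, PTH, Phos results to be determined on a case-by-case basis", the decision resting with a study endocrinologist. Study Design (Treatment subjects) describes the laboratory findings that matter in these terms: "could exclude patients include an elevated PTH or hypercalcemia". It adds that "there will not be hard cutoff values for the labs". The screening section places this review after consent and before enrollment.

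**Historical controls.** Their two exclusions are "Any history of prior teriparatide or abaloperatide use" and "Use of denosumab in the past year". Table 2 lists no laboratory tests for cohort A, and the procedures checklist says "Blood will be drawn for eligibility screening, and HbA1c levels in treatment subjects only". Sources of Materials does list existing chart data for controls. For cohort B the entry is "Lab results and office notes (incl. eligibility criteria, demographic information, and dens fracture characteristics". No rule uses those results to screen a control.

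**Analysis.** Statistical Considerations makes percentage of bridging bone on CT the primary outcome, read by a radiologist blinded to group. It plans a regression/ANOVA analysis without naming covariates, and sets the pilot at 10 treated patients and 12 controls.

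**The concern.** In a comparison with historical controls, eligibility rules are the main protection of comparability. The plan already carries two treated exclusions over to controls: prior PTH-analog use and denosumab. It does not carry over the bone-disease exclusions or the only laboratory review. A control with one of these conditions counts as collar-alone experience, while a similar patient presenting today might never enter the treated group.

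Blinding the radiologist protects the reading of the scan, not the selection of the patients. With 22 patients in all, regression could correct little even if covariates were named, so the imbalance is best dealt with at eligibility. The pilot is meant to suggest efficacy and inform a randomized trial, so a selection difference could distort both the efficacy signal and the effect size carried into that trial.

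**Working it through.** **1. Criteria side by side**

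| Treated exclusion | Counterpart for controls |
|---|---|
| 6–10: skeletal radiation, osteosarcoma, Paget's disease, bone metastases or malignancy, hereditary risk | None |
| 11: prior teriparatide or abaloparatide | Yes (control exclusion 5) |
| 12: denosumab within a year | Yes (control exclusion 6) |
| 13: psychological impairment precluding collar adherence | None, but partly covered by required completion of 12 (±1) weeks of collar |
| 14: kidney stones, CMP, PTH, Phos, case by case | None |

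**2. The plan's own figure.** Statistical Considerations assumes non-union of 60% (control) and 20% (treated), alpha 0.05 and 80% power, and states 44 patients. Taking alpha as two-sided, the arcsine formula is n per group = 2(1.960 + 0.842)² / h², with h = 2·asin(√0.6) − 2·asin(√0.2) = 1.772 − 0.927 = 0.845. This gives 21.99, so 22 per group and 44 in total, as stated. The pooled normal formula gives 23 per group, 46 in total. The stated figure stands and does not depend on this point; its 60% and 40-point difference serve as the reference below.

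**3. Sensitivity of the control rate.** Let f be the share of controls who would have been excluded under 6–10 or 14, and r their non-union rate, with overall control non-union held at 60%. Then:

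- non-union in comparable controls = (0.60 − f·r) / (1 − f)
- shift = 0.60 − that value (positive favours the drug)

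Example: f = 0.30, r = 1.00 gives (0.60 − 0.30)/0.70 = 42.9%, a shift of +17.1 points. With r = 0.40 it is (0.60 − 0.12)/0.70 = 68.6%, a shift of −8.6 points.

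The documents give neither f nor r. Both ranges are assumptions.

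| f | Expected among 12 controls (12·f) | r = 40% | r = 60% | r = 80% | r = 100% |
|---|---|---|---|---|---|
| 5% | 0.6 | −1.1 | 0 | +1.1 | +2.1 |
| 10% | 1.2 | −2.2 | 0 | +2.2 | +4.4 |
| 20% | 2.4 | −5.0 | 0 | +5.0 | +10.0 |
| 30% | 3.6 | −8.6 | 0 | +8.6 | +17.1 |

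**4. Granularity.** One control is 1/12 = 8.3 points of control non-union, against an assumed difference of 60 − 20 = 40 points.

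**5. Scale.** These figures are on non-union because that is the only scale for which the plan gives rates. It gives no mean or spread for percentage of bridging bone, so the effect on the primary outcome cannot be sized from the documents.

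**The case against.** The strongest case against has four parts.

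- **The screen is for drug safety.** The Risks/Benefits and Drug Information sections justify the calcium, stone and osteosarcoma-risk criteria by hazards of the drug, which controls never received. That is true, but the reason for a filter does not change its effect: applied to one group, it selects that group.
- **The direction is not documented.** The documents never say that calcium, PTH, phosphate or stones affect dens union. They describe this blood work as a way to assess osteoporosis, and they tie HbA1c and DEXA to the ability to heal. That makes worse healing a plausible inference and no more. This part stands.
- **Other control rules may push the other way.** Required collar completion can remove early failures from the controls, and a cohort A research CT may come years after injury. The net direction of all selection differences therefore cannot be read from this one. This stands too, but opposing biases of unknown size are no reason to leave a correctable one in place.
- **The match can only be partial.** Table 1 marks CMP, PTH and Phos as research-driven, so many controls may lack them. This stands and shapes the remedy.

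A reader might go further and infer that such patients remain only among controls and that the gap favours the drug by a definite amount. The documents do not support either step. The laboratory review is discretionary: abnormal values could exclude, and hypercalcemia leads to exclusion only if judged appropriate, so some affected patients may be treated. If subset non-union is assumed to be 70–90% with shares of 10–30%, the shift is 1.1 to 12.9 points, always for the drug. That is only because every assumed rate lies above 60%: at 60% it is zero, and below 60% it reverses. Nor do the documents say that reasons for exclusion go unrecorded. They are silent on it.

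**Conclusion.** The point holds as a comparability gap. Exclusions 6–10 and 14 have no counterpart among the historical controls, no named covariate corrects for this, and affected patients are preferentially retained among controls.

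The size and sign of the bias are unknown. It favours the drug only if these patients heal worse than the control average, which is plausible but not stated. Over the assumed ranges (share 5–30%, subset non-union 40–100%, overall control non-union 60%) the shift is about −9 to +17 points. Even one misplaced control is visible at 12 controls. The study's status as a pilot limits what rests on the result, but does not make the two selection rules equivalent. The gap is worth closing because the remedy is inexpensive.

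**What to change.** 1. In the criteria for Historical Comparison Subjects, apply exclusions 6–10 and a chart version of exclusion 14 to both control cohorts. The chart version uses recorded diagnoses (kidney stones, hyperparathyroidism or another hypercalcemic disorder) and whatever calcium, phosphate, metabolic-panel and PTH results exist from the fracture episode.
2. Have the study endocrinologist make this judgement without seeing healing images, and record each control as passed, failed or not screened.
3. Record the specific reason for each treated exclusion under 14 as it happens, since discretionary decisions are hard to reconstruct later.
4. Keep controls with missing laboratory results, flag them and report how many there are.
5. Repeat the primary comparison of percentage of bridging bone without controls who would have failed the screen. Repeat it also without unscreened controls, but only if enough remain; dropping them all could leave few of the 12.
6. State the partial match as a limitation.

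**Cost.** Protocol wording and some chart abstraction, with no new visit or blood draw. Lab results and office notes are already listed as control sources, although the procedures text for cohort B does not mention laboratory results and should be brought into line. One or two controls may be lost, and PTH data will be incomplete.
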